#### **I. Scientific and Substantive Changes:**

#	Section	Comments
1.	Synopsis	Due to delays in clinical treatment as a result of COVID-19, timelines of treatment and staging procedures window needs to be increased. Post visit follow up window has been increased to 4 weeks (+6 weeks).
2.	2.2	The anticipated study duration was changed to 21 months (1 year and 9 months) to accurately reflect the timeline for collecting new and existing cancer cases. Due to COVID-19 disruptions to patient referrals, routine clinic visits, and provider illnesses, this study should be extended by one year to capture patient volumes and patient cases presenting to sites as clinic activities begin to resume.
3.	3.3.1	Due to the one-year extension of the study, additional enrollment per site is expected. Thus, the maximum participant enrollment has been changed from 200 participants to 400 participants.
4.	3.3.3	Due to the increase of maximum participants, the Expected Enrollment Demographics table has been updated.

#### **II. Administrative and Editorial Changes:**

#	Section	Comments
5.	Global	The version number and date were updated from version 2 dated 02OCT2019 to version 3 dated TBD.
6.	Appendix III	The AMC Data and Safety Monitoring plan was updated from version 6.0 to the current version (9.0). Key revisions include: the addition of an introduction to address the variety of systems the AMC uses for individual trials; changes to the data entry systems used by domestic AMC trials (OPEN/Rave) activated September 1, 2020 and later; participation with a

#	Section	Comments
		single IRB for new domestic AMC protocols; updated procedures for data reporting, determination of requirements for DSMB review, and safety review/pharmacovigilance; and administrative changes (updates to document organization, external links, and group terminology) and to state that the IRB review plan is identified in the protocol, as the AMC is opening international studies subject to review/requirements per their respective regions.

## PROTOCOL SYNOPSIS

Title:	Prospective observational study of the frequency of site-specific new and existing cases of cancer in People Living with HIV/AIDS in Latin America
Design:	Observational prospective cohort
Accrual Target:	Minimum of 10 cases per participating site; maximum of 400 participants across all centers
Regulatory Status:	Pursuant to national requirements for each participating site
Population:	Participants presenting to HIV treatment programs or cancer treatment programs at collaborating sites, with both HIV and cancer, which may include either a history of malignancy or current diagnosis.
Regimen:	Non-interventional. Data collection will occur via survey procedures and/or medical record review at screening, enrollment, and if available, at 4 weeks following enrollment (+6 weeks).
Anticipated Trial Duration:	1 year, 9 months
Primary Objective:	To determine the frequency of new and existing diagnosed HIV-associated cancers presenting at participating clinical sites in Latin America, based on all presenting cancers (new diagnosis, recurrence, and surveillance cases as defined in Section 3.1.2 )
Secondary Objectives:	

• Obtain information on the use of diagnostic testing and treatment for the cohort of diagnosed cancers in people living with HIV/AIDS.

• To collect current information on participant characteristics for diagnosed cancers in people living with HIV/AIDS (e.g., ART regimen, CD4 count, viral load, etc.)

Exploratory Objectives	

• To determine the timelines and requirements for protocol review and approval at the local, regional, and national level.

• To familiarize local sites with the online data entry systems used by the AMC.

## LIST OF ABBREVIATIONS

ACSR	AIDS and Cancer Specimen Resource
AE	Adverse event
AIDS	Acquired immunodeficiency syndrome
AMC	AIDS Malignancy Consortium
ANC	Absolute neutrophil count
ART	Antiretroviral therapy
CBC	Complete blood count
CDC	Centers for Disease Control and Prevention
CDUS	Clinical Data Update System
CIA	Chemiluminescent Immunoassay
CR	Complete response
CRF	Case report form
CTEP	Cancer Therapy Evaluation Program
CTEP-AERS	Cancer Therapy Evaluation Program Adverse Event Reporting System
DARF	Drug accountability record form
DHHS	Department of Health and Human Services
DNA	Deoxyribonucleic acid
DSMB	Data and Safety Monitoring Board
ECOG	Eastern Cooperative Oncology Group
EIA	Enzyme Immunoassay
FDA	Food and Drug Administration
FTP	File transfer protocol
HIV	Human immunodeficiency virus
IEC	Institutional ethics committee
IC	Institution and Center
IRB	Institutional review board
IND	Investigational new drug
KPS	Karnofsky performance score
NCI	National Cancer Institute
ODMC	Operations and Data Management Center

PCR	Polymerase chain reaction
PLWHA	People living with HIV/AIDS
PR	Partial response
REB	Research ethics board
RNA	Ribonucleic acid
SAE	Serious adverse event
SOP	Standard Operating Procedure
WHO	World Health Organization

## **1.0 OBJECTIVES**

### **1.1 Primary Objective**

To determine the frequency of new and existing diagnosed cancers in PLWHA presenting to participating clinical sites in Latin America, based on all presenting cancers (new diagnosis, recurrence, and surveillance cases as defined in [Section 3.1.2](#)).

### **1.2 Secondary Objectives**

- 1.2.1 Obtain information on the use of diagnostic testing and treatment for the cohort of diagnosed HIV-associated cancer participants.
- 1.2.2 To collect current information on participant characteristics for diagnosed HIV-associated cancers (e.g., ART regimen, CD4 count, viral load, etc.)

### **1.3 Exploratory Objectives**

- 1.3.1 To determine the timelines and requirements for protocol review and approval at the local, regional, and national level.
- 1.3.2 To familiarize local sites with the online data entry systems used by the AMC.

## **2.0 BACKGROUND**

### **2.1 Study Disease**

The AIDS Malignancy Consortium (AMC), as part of its international agenda, is extending its research network into Latin America (LA) and has added 4 sites in the region as of September 1, 2018. Building on lessons learned in the site selection and implementation of clinical trials in Africa, the AMC will utilize a non-interventional, registration-type study to prospectively gather information over a limited time frame on the presentation, evaluation, and treatment of participants newly presenting with HIV-associated cancers (new diagnosis or relapsed/recurrent, excluding dysplasia) that will help to inform the development of future AMC therapeutic trials in LA.

The AMC expansion into LA is supported by the following observations: first, HIV remains common in the region; second, successful HIV treatment programs have resulted in longer survival among people living with HIV/AIDS (PLWHA) and leading to increased cancer incidence; third, regional investment in research and treatment of cancer, and HIV-related malignancy in specific, has been limited. In 2015, there were an estimated 2 million PLWHA in LA, 100,000 new HIV infections, and 50,000 AIDS related deaths. This region has been successful in implementing HIV diagnostic and treatment programs, with an estimated 70% of PLWHA diagnosed, and 44% of eligible adults treated with anti-retroviral therapy (ART). A recent analysis comparing Latinos in LA versus North America found this population had better continuity of treatment, but conversely had higher mortality, particularly in the first year on ART. Quantifying the impact of cancer on HIV outcomes is hobbled by a dearth of data in this area.

Publications about cancer amongst PLWHA in LA are very limited. The most comprehensive study to date described a cohort of 428 patients with 455 cancers or pre-cancerous lesions amongst the 3372 patients within the Caribbean, Central and South America Network for HIV Research (CCASAnet). Of the 406 cancers, 82% were AIDS-defining, predominantly Kaposi sarcoma and non-Hodgkin lymphoma, and 18% were Non-AIDS Defining (NADC), predominantly Hodgkin's lymphoma and skin cancers. Approximately half the patients received cancer-specific treatment (chemotherapy, radiotherapy, or combination), with under half of patients reported cured, one-third persistent, and the remainder with unknown outcome. However, improving these outcomes is presently limited by a lack of clinical trials for HIV related cancers in the region.

A Lancet Oncology Commission in 2013 found several hurdles to clinical cancer research in the region, including too few cancer care specialists, limited local expertise in research, and fragmented healthcare systems. A 2015 report by the same body optimistically noted an increased number of oncologists, expansion of cancer registries, and improved national policies and access to care. However, the report still highlighted fragmentation within the healthcare system between urban and rural settings and across the public and private health systems. Further, it was emphasized that there remained inadequate cancer research expertise and infrastructure. This finding in particular highlights the importance of the AMC's proposal to develop research sites in LA, but also highlights the importance of understanding the movement of patients through the health care system to ensure the success of this effort.

The expansion into Sub-Saharan Africa (SSA) emphasized that a structured understanding

of the health delivery services at new collaborating sites is critical to successful partnerships. Building on our prior experience and lessons learned from SSA, allowing targeted strategic investment in education and infrastructure, we propose a non-interventional registration study that will provide practical information about HIV and cancer care, research infrastructure, and the management of HIV+ cancer patients, while also introducing the new AMC sites to the group's online data entry system.

## 2.2 Study Design and Rationale

This protocol will develop a prospective cohort of newly diagnosed and previously diagnosed cancers in each site's HIV patient populations.

Following local/regional/national regulatory approval of this protocol, sites will be asked to prospectively capture cancer diagnoses in the setting of HIV infection, that present to the sites. The convenience sampling used in this protocol will only capture participants presenting at participating centers and will not actively identify participants in historical records. Data collection will occur over a period of 1 year, and 9 months. All participants presenting to sites with a diagnosis of HIV-associated cancer will be asked to participate. All patients presenting to the clinic with HIV and a diagnosis of malignancy will be recorded on a screening list. In participants who consent to participate in the data collection, data captured will include, but not be limited to, the following:

**Table 2-A: Model Participant Data Set**

Demographics	Age, sex, etc.
HIV Care	Whether current HIV care is being received at the enrolling institution, current ART regimen, date of diagnosis, method of diagnosis, current OIs, current medications, recent viral load, CD4 count
Status of Diagnosis	New Diagnosis, pre-treatment phase, and treatment phase Prior Diagnosis, in remission (within 5 years of initial diagnosis) Prior Diagnosis, recurrent, pre-treatment, treatment phase, or no treatment planned
Cancer Diagnosis	Cancer diagnosis, date cancer diagnosed, diagnostic methods (cytology, histology), pathology performed, date of pathology, staging, staging methods (clinical, radiographic, surgical), date(s) of staging (new and recurrent cancer only), current ECOG PS, current laboratory values
Cancer Treatment Plan	Detailed prior/planned treatment (e.g., chemotherapy, radiation, surgery, or best supportive care/watchful waiting). Whether current cancer care is being received or will occur at the enrolling institution. Timeline of planned treatment (i.e., start date).

For participants initiating therapy (new or recurrent) or currently under treatment, a short interval follow-up (approximately 1-3 months), will be used to ascertain the current vital status, and current state of planned cancer therapy. The data collected at this later time point will be limited, as the intent of this data capture is to ascertain the relationship between planned therapy and therapy received. These data will include any cancer-specific therapy initiated since registration, the start date of that therapy, and whether the therapy has had significant delays to initiation or interruptions of therapy.

Please see [Section 7.2](#) for specific data to be collected during this protocol.

### **3.0 PARTICIPANT SELECTION**

A rostered AMC investigator (CTEP-registered physician investigator or Non-Physician Investigator) or delegated clinical staff (CTEP-registered Associate Plus) must document that each protocol participant meets all stated eligibility criteria. Participating sites must have documentation that each eligibility requirement is satisfied prior to participant enrollment. In compliance with CTEP policy, no exceptions to eligibility criteria will be granted under any circumstance.

NOTE: Institutions may use this section of the protocol as an eligibility checklist for source documentation if it has been reviewed, signed, and dated before registration/randomization by the study investigator. If used as source documentation, this checklist must be printed, the investigator must check each item to document their assessment that the participant meets each eligibility criterion, and the completed checklist must be maintained in the participant's chart.

Participant ID Number: S008 - \_\_\_\_\_ - \_\_\_\_\_

Participant's Initials (L, F, M *[optional]*): \_\_\_\_\_

NOTE: All questions regarding eligibility should be directed to the study chair.

#### **3.1 Eligibility Criteria**

3.1.1 HIV positive. Documentation of HIV-1 infection by means of any one of the following:

- Documentation of receipt of ART by a licensed health care provider (Documentation may be a record of an ART prescription in the participant's medical record, a written prescription in the name of the participant for ART, or pill bottles for ART with a label showing the participant's name);
- HIV-1 RNA detection by a licensed HIV-1 RNA assay demonstrating >1000 RNA copies/mL, and supported by a licensed screening antibody and/or HIV antibody/antigen combination assay;
- Any licensed HIV screening antibody and/or HIV antibody/antigen combination assay confirmed by a second licensed HIV assay, such as a HIV-1 Western blot confirmation or HIV rapid multispot antibody differentiation assay.

Note: The term "licensed" refers to a kit that has been certified or licensed by an oversight body within the participating country and validated internally.

WHO (World Health Organization) and CDC (Centers for Disease Control and Prevention) guidelines mandate that confirmation of the initial test result must use a test that is different from the one used for the initial assessment. A reactive initial rapid test should be confirmed by either another type of rapid assay or an E/CIA that is based on a different antigen preparation and/or different test principle (e.g., indirect versus competitive), or a Western blot or a plasma HIV-1 RNA viral load.

3.1.2 Must have a current or prior (within the last 5 years) diagnosis of cancer – but there is no restriction of the number or type of prior treatments. Participants will qualify under one of three categories:

- New diagnosis – no prior treatment for current malignancy. May be prior to, or currently receiving the first line of therapy.
- Prior diagnosis (within 5 years), in remission – Not currently on cancer treatment other than cART. Prior treatment for malignancy can include surgery, radiation, or chemotherapy (or cART initiation in KS). No restriction on number of prior lines of therapy.
- Prior diagnosis, recurrent – Considering or currently receiving treatment that is not first line. No restriction on the number of prior lines of therapy

\_\_\_\_\_ 3.1.3 Age > 18 years. Date of birth and age should be determined based on best possible information or documentation available.

\_\_\_\_\_ 3.1.4 Ability to understand and the willingness to provide informed consent document.

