### **3.2 Exclusion Criteria**

Participants not meeting all criteria above in [Section 3.1](#) are ineligible.

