7.2.3 Current ECOG performance status (see [Appendix II](#))

7.2.4 Estimated life expectancy

7.2.5 Status of cancer diagnosis (one of the following)

- New diagnosis, pre-treatment phase
- New diagnosis, treatment phase
- Prior diagnosis, in remission (within 5 years of initial diagnosis)
- Prior diagnosis, recurrent, pre-treatment phase
- Prior diagnosis, recurrent, treatment phase
- Prior diagnosis, recurrent, no treatment planned

7.2.6 For participants with a new diagnosis (pre-treatment or treatment), the following will be collected:

7.2.6.1 Cancer diagnosis, date of diagnosis, method of diagnosis (cytology, histology), type of pathology performed (H&E, immunohistochemistry, other), data of pathology, staging, staging methods (clinical, radiographic, surgical), date(s) of staging, most recent laboratory values (this would

include complete blood count, renal and liver function, electrolytes, CD4 count, and HIV viral load).

7.2.6.1 Detailed planned or current treatment. This should encompass surgical interventions, radiotherapy, and chemotherapy (agent names), including dates of planned or current therapy, and whether cancer care is being received or will occur at the enrolling institution.

7.2.7 For participants with a prior diagnosis in remission, the following will be collected:

- Cancer diagnosis, date of diagnosis
- Current method of post-treatment surveillance (clinical, laboratory, radiographic), and current schedule of follow-up with this center, current laboratory values (this would include complete blood count, renal and liver function, electrolytes, CD4 count, and HIV viral load).
- Prior method of diagnosis (cytology, histology), pathology performed, date of pathology, staging, staging methods (clinical, radiographic, surgical). Records from a prior diagnosis/treatment should be requested, but if they are unavailable, participant report will be sufficient.
- Prior treatment. This should encompass surgical interventions, radiotherapy, and chemotherapy. Records from a prior diagnosis/treatment should be requested, but if they are unavailable, participant report will be sufficient.

7.2.8 For participants with a prior diagnosis, recurrent (pre-treatment, treatment, or no planned treatment) the following will be collected:

- Initial cancer diagnosis, date of diagnosis

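### Section 3.1.2 admits recurrent patients only if treatment is considered or under way, although other sections expect enrolled patients with none planned; 7.2.5 also lacks a status for a new diagnosis with no treatment planned

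*Combined protocol and SAP*

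**What the plan says.** **Who may be enrolled.** Section 3.1.2 sets three qualifying categories: new diagnosis, prior diagnosis in remission, and prior diagnosis with recurrence. The recurrent category is described as "Considering or currently receiving treatment that is not first line". Section 3.0 adds that "no exceptions to eligibility criteria will be granted under any circumstance". Section 3.2 declares ineligible "Participants not meeting all criteria above" in 3.1.

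**Who is expected in the data.** The status row of Table 2-A lists "Prior Diagnosis, recurrent, pre-treatment, treatment phase, or no treatment planned". Section 7.2.5 has the same status among its six options. Section 7.2.8 sets out the enrolment data for that group, including why no further therapy is given. Sections 2.2 and 7.1 say that all presenting patients with HIV and cancer are to be invited, with no condition on treatment.

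**What is counted.** The primary objective (1.1) covers "new diagnosis, recurrence, and surveillance cases as defined in" Section 3.1.2. Section 8.0 defines recurrent status by progression after a prior therapy, without reference to current treatment. It includes best supportive care in the frequency of new and existing cases. It follows new cases until first-line therapy is finished or the patient is discharged without cancer treatment being planned.

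**New diagnoses.** Sections 7.2.5 and 7.2.6 and the status row of Table 2-A recognise only a pre-treatment and a treatment phase. Section 8.0 defines the pre-treatment phase as one in which treatment is planned.

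**The concern.** The eligibility text and the data-collection text answer the same question differently: may a patient with recurrent cancer and no planned treatment be enrolled? A site using Section 3 as its signed checklist would say no. A site working from 7.2.5 and 7.2.8 would say yes. If sites differ, the patients described differ by site for a reason unrelated to the disease. Data on patients who were never enrolled cannot be recovered later.

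The group at risk matters to this study. Section 1.2 makes the use of diagnostic testing and treatment a secondary objective, and Section 2.1 says that the results should inform future therapeutic trials in the region. Patients for whom nothing further is offered, and the reasons why, belong in that picture. For new diagnoses the problem is one of coding: the patient may be enrolled, but no listed status describes the situation.

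**Working it through.** No figure in the plan depends on this point, so the check sets the passages side by side.

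**Step 1: match case types to rules.**

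| Situation at presentation | Category in 3.1.2 | Status in 7.2.5 | Counted under Section 8.0 |
|---|---|---|---|
| New, treatment planned | yes | yes | yes |
| New, on treatment | yes | yes | yes |
| New, none planned | not excluded | **none** | yes, until discharge |
| Prior, in remission | yes | yes | yes |
| Recurrent, treatment planned | yes | yes | yes |
| Recurrent, on treatment | yes | yes | yes |
| Recurrent, none planned | **no, read literally** | yes | yes |

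There are seven situations and six statuses. One status has no eligibility category, and one counted case type has no status.

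**Step 2: test readings that would remove the conflict.**
- *Considering* could cover a patient who weighed treatment and declined it. But 7.2.8 also lists lack of options and lack of benefit as reasons.
- The plan might change after enrolment. But 7.2.5 and 7.2.8 are recorded at enrolment.
- The statements in 3.1.2 that there is no restriction concern prior treatments and lines of therapy, not the current plan.
- The remission category cannot take these patients, because Section 8.0 ends remission at progression.
- For new diagnoses, 3.1.2 says that the patient may be before or in first-line therapy. That is permissive, so the gap is a missing status and not an exclusion.

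**Step 3: trace each result to a possible source.** Under 2.2, 7.1 and 11.1 the screening list covers all presenting patients. It holds age, sex at birth and cancer type, and is not linked to enrolment.
- Combined number by site and cancer type: the list can supply it, so it need not depend on 3.1.2.
- Number of new cases: unchanged. Recurrent patients are not new cases, and a new patient without a fitting phase is still a new diagnosis.
- Number of existing cases: the list holds no disease status. A count from enrolled participants is too low by the number of recurrent patients turned away.
- Treatment description and reasons for no therapy: available only from enrolled participants, so affected.

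Section 9.1 does not say which source feeds which result.

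**Step 4: size.** The documents give no share of patients with no treatment planned. The following ranges are pure assumptions, given only for scale.
- Recurrent patients not enrolled = recurrent share × share of those with none planned. From 0.10 × 0.10 = 1% to 0.30 × 0.50 = 15%, or 4 to 60 per 400 cases.
- New patients without a status = new share × share of those with none planned. From 0.30 × 0.05 = 1.5% to 0.60 × 0.20 = 12%, or 6 to 48 per 400 participants.

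The 400 is the enrolment ceiling in 3.3.1. The first range applies only if every site reads 3.1.2 literally.

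**The case against.** The intent is fairly plain, and most of the protocol points one way. Sections 2.2 and 7.1 invite everyone who presents, 7.2.5 offers an explicit status for recurrent patients with none planned, and Section 3.0 says "All questions regarding eligibility should be directed to the study chair". Wholesale exclusion is therefore unlikely. This stands, and it lowers the expected harm. It does not remove the conflict: the chair is consulted only if a site sees a question, and the same section rules out exceptions.

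On new diagnoses, the treatment-plan row of Table 2-A already includes "chemotherapy, radiation, surgery, or best supportive care/watchful waiting", the data set in 2.2 is open-ended, and the case report forms are not part of these documents. So the information might still be captured. This stands in part: a treatment-plan entry is not a status, and 7.2.6 asks only about surgery, radiotherapy and chemotherapy, with no reason for giving none.

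A reader might infer three stronger points, which the documents do not support.
- *The primary count and its Poisson interval are biased.* Section 9.1 estimates the combined number of new and existing cases, and the screening list can provide it.
- *The proportion of new cases is inflated, or all recurrent patients will appear treated.* Neither percentage is a planned statistic. Section 8.0 and the primary estimate in 9.1 use counts, and the secondary endpoint is the frequency of tests and regimens.
- *Appendix I confirms that recurrent patients with none planned are enrolled.* Its footnote waiving the week 4 contact is not specific to recurrent disease and could equally refer to participants in remission.

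**Conclusion.** The inconsistency is real, minor to moderate, and cheap to remove. Read literally, 3.1.2 excludes a group that Table 2-A, 7.2.5 and 7.2.8 plan to describe and Section 8.0 counts. At a site applying it that way, best supportive care and the reasons for no therapy in recurrent disease are under-recorded in the secondary description of treatment, and the 7.2.8 reason item would stay empty at enrolment. Any existing-case count drawn from enrolled participants would be too low. New patients with no treatment planned have no fitting status anywhere.

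The size cannot be determined. It depends on how many sites read 3.1.2 literally and on shares that the documents do not give. The conclusion that the combined count is probably safe rests on its being taken from the screening list, which 7.1 and 11.1 indicate but 9.1 does not state.

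**What to change.** 1. Reconcile the recurrent line of 3.1.2 with Table 2-A, 7.2.5, 7.2.8 and Section 8.0, so that recurrent patients with no treatment planned can be enrolled in this non-interventional registration. This concerns enrolment wording only and touches no treatment decision.
2. Add a status *New diagnosis, no treatment planned* to 7.2.5 and to the status row of Table 2-A, and reuse the reason-for-no-therapy item of 7.2.8 in 7.2.6.
3. In 9.1, state that the total count comes from the screening list (7.1 and 11.1), and that treatment descriptions come from enrolled participants and are shown by 7.2.5 status.

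The cost is minor wording in an amendment, one extra response option, one reused question and a few more enrolled patients.
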